7.5 Dose Modifications

The dose modification should be performed for the drug toxicity or underlying disease conditions. Guidelines (Refer [Table 2](#) and [3](#)) are intended to be applied when the investigator determines the event related to Tenalisib. Please note the dose modifications provided below should be used as a guidance and should be determined as per PI's clinical judgement.

Patients may resume Tenalisib, provided that the toxicity has resolved to Grade ≤ 2 or baseline and there is no clinical or radiographic evidence of disease progression. If study drug is delayed > 2 weeks because of an adverse event, strategy of re-initiation of study drug should be discussed with medical monitor.

At the discretion of the Investigator, a dose re-escalation may be permitted for patients who previously had a dose reduction. Holidays from study drug are discouraged. Any patient in whom similar toxicity recurs at the reduced dose should be discontinued from further Tenalisib treatment. Note: In exceptional case, a patient may be allowed following a careful assessment of benefit and risk by the investigator and with approval from the medical monitor.

Table 2: Dose Modifications for Hematologic Toxicity

Worst CTCAE Grade Toxicity	Action to be Taken
HEMATOLOGIC	
Neutropenia (ANC)	
Grade 3 $1.0 \times 10^9 / L < ANC \geq 0.5 \times 10^9 / L$	Maintain dose level. Monitor ANC at least weekly.
Grade 4 $0.5 \times 10^9 / L < ANC$	First incidence: Withhold* dose until resolved to \leq Grade 2 or baseline. Monitor ANC at least weekly. Resume treatment at the same dose level. Subsequent occurrence: Hold dose until resolved to \leq Grade 2 or baseline. Consider growth factor support. Resume treatment at the reduced dose level (Tenalisib 400 mg BID) if warranted.
Grade 3 Febrile neutropenia $ANC < 1000 / mm^3$ with a single temperature of $> 38.3^{\circ}C (101^{\circ}F)$	Withhold* dose until resolved to \leq Grade 2 or baseline, consider growth factor support, then reduce by 1 dose level (Tenalisib 400 mg BID), if

or a sustained temperature of $\geq 38^{\circ}\text{C}$ (100.4°F) for more than one hour.	warranted. If the ANC is $<1 \times 10^9/\text{L}$ ($1000/\mu\text{L}$) before therapy, the dose shall not be modified as long as $\text{ANC} > 0.5 \times 10^9/\text{L}$.
Thrombocytopenia	
Grade 3 thrombocytopenia with Grade 1 bleeding	Maintain Tenalisib dose. Monitor platelet count at least weekly.

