Grade 3 thrombocytopenia with Grade 2 bleeding OR Grade 4 thrombocytopenia ($20.0 \times 10^9/\text{L} < \text{PLT}$)	1st occurrence: Withhold** dose until to \leq Grade 2 or baseline or resolution of bleeding. Consider platelet transfusion as necessary. Resume treatment at the same dose level. Subsequent Occurrences: Withhold dose until to \leq Grade 2 or baseline or resolution of bleeding. Consider platelet transfusion as necessary. Resume treatment at the reduced dose level (Tenalisib 400 mg BID) if warranted. Doses should not be modified if Grade 4 thrombocytopenia is present at baseline.

* The treatment should be permanently discontinued if withhold of study drug due to drug related toxicity is for > 28 days unless approved by medical monitor.

** Patient receiving concomitant medication (e.g. anti-platelets, aspirin, or low molecular weight heparin) should be discussed with the medical monitor for further management.

Table 3: Dose Modifications for Non-Hematologic Toxicities

NON-HEMATOLOGIC	Action to be Taken

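### Read literally, the platelet hold row in Table 2 lets Tenalisib restart at Grade 4 platelets once bleeding has stopped

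*Combined protocol and SAP*

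**What the plan says.** Three statements in protocol Section 7.5 bear on restart after a platelet hold.

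- **General restart condition (text before the tables).** "Patients may resume Tenalisib, provided that the toxicity has resolved to Grade" 2 or lower, or to baseline, and there is no evidence of progression. Bleeding is not mentioned as an alternative.
- **Label of the platelet hold row (Table 2).** "Grade 3 thrombocytopenia with Grade 2 bleeding OR Grade 4 thrombocytopenia". A Grade 4 count is a reason to hold on its own, with or without bleeding.
- **Action cell of the same row.** Both triggers share one cell. On first occurrence the drug is withheld until the count is Grade 2 or lower "or baseline or resolution of bleeding. Consider platelet transfusion as necessary. Resume treatment at the same dose level". For later occurrences the release is the same, but the restart is at 400 mg BID if warranted. Patients who had Grade 4 thrombocytopenia at baseline are exempt from modification.

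The row above it, for Grade 3 platelets with Grade 1 bleeding, says "Maintain Tenalisib dose. Monitor platelet count at least weekly". The section also states that "the dose modifications provided below should be used as a guidance and should be determined as per" the investigator's clinical judgement, and that the tables apply to events judged related to Tenalisib.

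**The concern.** The row joins two triggers with a plain OR and three releases with a plain OR, and does not say which release belongs to which trigger. Bleeding resolution is a sensible release when bleeding is what turned a Grade 3 count into a hold. It is not an obvious release when the hold is for the count itself.

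An investigator who follows the cell as printed could put a patient back on the same dose while the toxicity behind the hold is unchanged. One who follows the general condition, or rereads the row label, would go on holding. Safety and tolerability is the first objective in Section 2, so a restart rule that gives two answers for one patient deserves correction.

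**Working it through.** No figure in the plan is at issue and no arithmetic applies, so the check sets the three statements side by side. Assume the patient was not Grade 4 at baseline, has not progressed, and is at the first occurrence.

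| Patient state when restart is considered | Row's release | General condition, Section 7.5 | Row's trigger |
|---|---|---|---|
| Count Grade 2 or lower, or at baseline; bleeding stopped | Restart | Restart | Not met at Grade 2 or lower |
| Held for Grade 3 with Grade 2 bleeding; bleeding stopped; count still Grade 3, not baseline | Restart | Hold | No longer met |
| Held for Grade 4 with bleeding; bleeding stopped; count still Grade 4 | Restart | Hold | Still met: hold |
| Grade 4, never bled | Bleeding alternative has no clear meaning; the count sensibly governs | Hold | Still met: hold |

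1. **First line.** The release and the general condition agree.
2. **Second line.** The row departs from the general condition, but it has a rationale. Once bleeding has stopped the trigger is gone, and the adjacent row keeps dosing at Grade 3 even with Grade 1 bleeding. This is a defensible exception that the text does not mark as one.
3. **Third line.** This is the error. The release permits restart at the same dose, while both the general condition and the row's own label say hold. A patient held for Grade 3 with bleeding who then falls to Grade 4 belongs on this line too, because Table 2 is keyed to "Worst CTCAE Grade Toxicity".
4. **Fourth line.** No conflict is claimed here.

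**Do the available readings remove the conflict?** There are two candidates.

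- *Section 7.5 as a floor under every restart.* This bars restart at Grade 4. But restart would then always need Grade 2 or lower or baseline, which the cell already lists, so the bleeding alternative would never have any effect.
- *Distributive reading: count recovery releases the Grade 4 trigger, bleeding resolution the Grade 3 trigger.* This settles the third line, but still departs from Section 7.5 on the second.

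Neither reading is stated, and neither makes every clause effective while agreeing with the rest of the section.

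**Comparison within Table 2.** There are five hold instructions. The three for neutropenia (Grade 4 first, Grade 4 subsequent, febrile) release only on Grade 2 or lower or baseline; for example, "First incidence: Withhold* dose until resolved to" that level. The two for platelets (first and subsequent) add the bleeding alternative: 3 + 2 = 5. The looser release is confined to the platelet row.

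**The case against.** The strongest defence is that a careful reader would not restart this patient. The general condition comes before the tables and names no exception, so the two can be followed together. A patient restarted at Grade 4 would at once meet the row's trigger again. Matching the count release to the count trigger and the bleeding release to the bleeding trigger is natural. The row is also loosely drafted: its Grade 4 cut-off is printed with the inequality reversed, which everyone reads in the intended sense, so strict parsing of the next cell may seem selective.

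Much of this stands as to consequence. It makes harm unlikely and keeps the point minor. It does not remove the defect, because each rescue needs a rule the text does not give and leaves a clause idle or a departure unmarked.

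A reader might also infer more than the documents support:

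- *That restart could happen with no platelet count because the protocol requires none.* Section 6.3 and Table 1 leave scheduled blood counts to standard of care. Monitoring in Table 2 is driven by events, though, and the adjacent row asks for weekly platelet counts. A hold under this row itself starts from a count.
- *That the row is unusual in giving no count interval during the hold.* Among the five hold instructions, only the first incidence of Grade 4 neutropenia states weekly counts. The next one, "Subsequent occurrence: Hold dose until resolved to" Grade 2 or baseline, gives none.
- *That restart at Grade 3 after bleeding stops is also an error.* It fits the adjacent row and only needs marking as an exception.

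**Conclusion.** The row is wrong as written in one patient state: bleeding stopped, count still Grade 4, not at baseline. There the printed release allows a same-dose restart that Section 7.5 and the row's own trigger forbid.

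Severity is minor. The tables are guidance under investigator judgement and apply only to events considered related to Tenalisib. Patients on anti-platelets, aspirin or low molecular weight heparin are referred to the medical monitor. No endpoint or analysis changes.

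The number of patients affected cannot be derived. The documents give no thrombocytopenia rate, about 50 patients are expected, and Section 3.4.5 does not name thrombocytopenia among events reported with Tenalisib, so the state is probably rare. The conclusion rests on reading the cell literally and on the absence of any statement that the general condition overrides the table.

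**What to change.** Split the release by trigger.

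- **Grade 4 platelets:** withhold until the count is Grade 2 or lower, or at baseline. Keep the exemption for patients who were Grade 4 at baseline.
- **Grade 3 platelets with Grade 2 bleeding:** keep bleeding resolution as a release, provided the count has not fallen to Grade 4, and mark it as an exception to the general restart condition in Section 7.5.

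Two additions are optional and not part of the error: platelet counts at least weekly during the hold, to match the adjacent row, and a requirement that bleeding has also resolved before a Grade 4 restart.

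The cost is rewording one row, plus some longer holds in a section that discourages breaks in dosing. Restart after delays of more than 2 weeks for an adverse event is already to be discussed with the medical monitor. The 28-day discontinuation footnote carries a single asterisk that does not appear on the platelet row. If it is meant to cover platelets, a longer hold could reach it unless the medical monitor approves, so the revised row should say whether it applies.

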6.3 Treatment and Study Procedures

Patients will visit the study center every three months until documented disease progression or treatment discontinuation due to toxicity or consent withdrawal. During these visits, Tenalisib will be dispensed and medication compliance will be monitored. Safety and efficacy assessments will be done as mentioned below.

- Safety assessments:**

- Safety assessment will be done during the visits and AEs will be reported as required by the protocol.
- Concomitant medications may be administered as clinically indicated.
- A medication history should be reviewed at each clinic visit to assure no potential adverse events are noted.
- There are no specific safety labs or evaluations (including vitals, physical examinations, pregnancy tests and ECGs) required as per protocol. As part of SOC, laboratory tests or other evaluations can be done per Investigator's discretion. Adverse events (AEs, SAEs and deaths) will be recorded and reported for 30 calendar days after last dose or until a new anti-cancer treatment is initiated, whichever is earlier. After this period, only AEs, SAEs, or deaths assessed by the investigator as treatment related are to be reported.

- Efficacy assessments:**

- Disease assessments [e.g. radiological imaging (e.g. CT, PET-CT) or any other appropriate evaluation tool (e.g. mSWAT in case of skin involvement)] should be performed as part of SOC. These evaluations (e.g. measurement of lymph node, mSWAT) will not be recorded in the CRF, however, date of disease progression will be reported .

- Drug dispensing:**

- Patients will be given drug supply for 3 months.

Table 1: Schedule of Events

	Screening and Eligibility	Cycle 1	Cycle 4	Cycle 7 Through EOT	EOT	EOS ¹¹
Day	D-14 to D1	D1	D1	D1	-	-
Window period	-14	-	±7	±7	-	+30
Study Days	D-14 to D1	1 ¹	85	169	-	-
Informed Consent	X	-	-	-	-	-
Eligibility Confirmation	X	-	-	-	-	-
Demographics ²	X	-	-	-	-	-
Medical history ³	X	-	-	-	-	-
Vitals	-	SOC*	SOC*	SOC*	SOC*	-
Weight ⁴	X	SOC*	SOC*	SOC*	SOC*	-
Physical exam	-	SOC*	SOC*	SOC*	SOC*	-
ECOG Performance	X	SOC*	SOC*	SOC*	SOC*	-
Complete blood count	-	SOC*	SOC*	SOC*	SOC*	-
Chemistry	-	SOC*	SOC*	SOC*	SOC*	-
PT/INR	-	SOC*	SOC*	SOC*	SOC*	-
Urinalysis (routine)	-	SOC*	SOC*	SOC*	SOC*	-
Pregnancy test ⁴	-	SOC*	SOC*	SOC*	SOC*	-
12-lead ECGs	-	SOC*	SOC*	SOC*	SOC*	-
Disease assessment ⁵	-	SOC*	SOC*	SOC*	SOC*	-
Date of discontinuation ⁶	-	-	-	-	X	-
Drug Dispensing ⁷	-	X	X	X	-	-
Tenalisib treatment ⁸	-	X	X	X	-	-

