	
The patient will be closely monitored until the QTcF <500 msec and the QTcF has returned to <30 msec from baseline. Immediate attention to potassium and magnesium and other clinical factors such as oxygenation and ischemia should be addressed.
 
All cardiac events should be treated as per the local standard of care and referral to a specialist if clinically indicated. Any final decisions concerning dose modifications or permanently discontinuing the patient from study drug due to QTcF prolongation will occur after discussion with medical monitor.

OTHER NON-HEMATOLOGIC	Action to be Taken
Grade 1 or 2	None
Grade 3	Withhold Tenalisib dose until toxicity Grade ≤ 2 . Restart Tenalisib at one dose lower (Tenalisib 400 mg BID) if warranted.
Recurrence of grade 3 toxicity	Withhold Tenalisib dose until toxicity Grade ≤ 2 ; Restart Tenalisib at one dose lower or discontinue treatment
Grade 4	Withhold Tenalisib dose until toxicity Grade ≤ 2 ; Restart Tenalisib at one dose lower (Tenalisib 400 mg BID) or discontinue Tenalisib
Recurrence of grade 4 toxicity	Discontinue Tenalisib

*The treatment should be permanently discontinued if withhold of study drug due to drug related toxicity is for > 28-days unless approved by medical monitor.

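### Table 2's exemption for Grade 4 platelets at baseline has no bleeding condition, so Grade 2 bleeding in those patients meets no written hold

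*Combined protocol and SAP*

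**What the plan says.** Protocol Section 7.5, Table 2, has two thrombocytopenia rows.

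- Grade 3 platelets with Grade 1 bleeding: "Maintain Tenalisib dose. Monitor platelet count at least weekly".
- "Grade 3 thrombocytopenia with Grade 2 bleeding OR Grade 4 thrombocytopenia": withhold. The hold runs until Grade 2 or lower "or baseline or resolution of bleeding. Consider platelet transfusion as necessary". Treatment resumes at the same dose after the first occurrence, and at 400 mg BID if warranted after later ones.

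The action cell of the second row ends with the exemption: "Doses should not be modified if Grade 4 thrombocytopenia is present at baseline". The double-asterisk footnote asks for a discussion with the medical monitor when the patient takes aspirin, an anti-platelet drug or LMWH. It does not mention bleeding.

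Table 3 has default rows for other non-hematologic toxicity. Grades 1 and 2 call for no action. At Grade 3 the instruction begins "Withhold Tenalisib dose until toxicity Grade", with release at Grade 2 or lower. At Grade 4 the drug is withheld or discontinued.

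The introduction to Section 7.5 limits the tables to events judged related to Tenalisib and adds that "the dose modifications provided below should be used as a guidance", subject to the investigator's clinical judgement.

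**The concern.** Exempting a long-standing low count is sensible: if the count was already Grade 4 before treatment, a rule based on the count alone would hold the drug for something it did not cause. But the exemption shares a cell with a rule that also responds to bleeding, and it does not say which of the two it switches off. As written it switches off both. The patient with the lower platelet count then gets the less cautious instruction for the same bleeding.

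The stake is patient safety at the site. Under Section 6.3, "Patients will visit the study center every three months until documented disease progression", and laboratory tests are left to standard of care, so an investigator who hears of a bleed between visits is likely to turn to this table. Adverse event grading, the safety summaries and the progression date do not depend on it.

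**Working it through.** There is no figure to reproduce. The check applies each rule literally to related events and compares the results.

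| Platelets now | Grade 4 at baseline? | Bleeding | Rule that applies | Instruction |
|---|---|---|---|---|
| Grade 3 | No | Grade 1 | Table 2, first thrombocytopenia row | Maintain, weekly count |
| Grade 3 | No | Grade 2 | Table 2, second row | Withhold |
| Grade 4 | No | Grade 2 | Table 2, second row | Withhold |
| Grade 4 | Yes | Grade 2 | Table 2 exemption; Table 3 default | No modification; no action |
| Grade 4 | Yes | Grade 3 | Table 2 exemption; Table 3 default | No modification; withhold |
| Grade 4 | Yes | Grade 4 | Table 2 exemption; Table 3 default | No modification; withhold or discontinue |

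1. Rows two and four have the same bleeding. Row four has the lower count and is the one not held. This is the inversion.
2. Could another rule hold the drug in row four? The double-asterisk footnote sets no bleeding condition. The advice in Section 3.4.5 to interrupt at Grade 3 or higher names liver enzymes, skin reactions, neutropenia and infection, not bleeding. Table 3 takes no action at Grade 2. None of them closes the gap.
3. In rows five and six, bleeding can be treated as an event in its own right under Table 3, which holds or stops the drug. The wording of the two tables is untidy together, but a workable instruction exists.
4. Does not modifying the dose include not withholding? Section 7.5 and both tables carry dose modification in their titles and list withholding among the actions, so the natural reading is yes.
5. Can the state occur? Sections 4.1 and 4.2 set no platelet threshold. Table 1 schedules no blood count at screening and leaves later ones to standard of care. Section 7.5 does not define baseline for patients rolling over from another study, but the inversion arises whichever value is used. The documents neither exclude such a patient nor show that one exists.

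**The case against.** The strongest case against the point is about scope. The tables are discretionary, and Section 4.3 lets the investigator stop treatment whenever continuing is not in the patient's interest. They apply only to related events, and Grade 4 platelets present from the start are an obvious other explanation for a bleed. The row has two triggers joined by OR, so a fair reader may take the exemption to cancel only the count trigger. All of this lowers the weight. It does not remove the inversion: Section 7.2 makes related the default unless there is a clear alternative explanation, and the favourable reading has to be supplied by the reader.

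A further objection is that the row already releases the hold at baseline, so for these patients the exemption changes little. That stands, and it shapes the fix: deleting the exemption would not be enough.

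Some stronger inferences are tempting but not supported.

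- *Grade 3 and 4 bleeding is also left uncovered.* Table 3 can be read as complementing Table 2 there.
- *The investigator must override the protocol to protect the patient.* Section 7.5 itself gives the decision to the investigator.
- *The exemption removes the weekly platelet counts required in the row above.* The Grade 4 row sets no count frequency for any patient, exempt or not.
- *The ANC exemption shows what was left out.* For a patient whose ANC was below 1 × 10⁹/L "before therapy, the dose shall not be modified as long as" the ANC exceeds 0.5 × 10⁹/L. That is a floor on the count, not a condition on symptoms. It shows only that a comparable exemption was given a limit.

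**Conclusion.** The point holds in a narrow form. For a patient with Grade 4 platelets at baseline and related Grade 2 bleeding, neither table holds Tenalisib, while the same row of Table 2 holds it for Grade 3 platelets with the same bleeding. The conclusion assumes that the exemption is read literally, that withholding counts as a modification, and that the bleed is judged related.

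Its size cannot be estimated. The documents do not say how many of the roughly 50 patients would have Grade 4 platelets at baseline. Even an assumed share would not give the risk, because the patient must also bleed at Grade 2, the event must be judged related, and the investigator must follow the sentence to the letter. The number affected may be zero. No endpoint, grading rule or analysis changes. This is a minor patient-safety correction, worth making because the text points the wrong way and is easy to repair.

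**What to change.** Replace the last sentence of the row with:

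*If Grade 4 thrombocytopenia was present at baseline, the dose need not be modified for the platelet count alone. With Grade 2 or higher bleeding, withhold Tenalisib until the bleeding resolves, whatever the baseline platelet count.*

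The closing clause is needed because the row's release at baseline could otherwise end the hold as soon as it began. The first sentence keeps the sensible purpose of the exemption.

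The cost is one sentence replaced by two, with no new test, visit or form. The downside is that a patient with long-standing Grade 4 platelets misses some doses while bleeding; the hold ends when the bleeding does and does not wait for platelet recovery. For Grade 3 bleeding the release is stricter than in Table 3, which allows a restart at Grade 2 or lower. The option in Table 3 to discontinue at Grade 4 should remain.

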Hepatic*	
Transaminitis
 
Grade 1-2 Transaminitis (ALT/AST $>1-3 \times \text{ULN}$ if baseline is normal; $1.5 - 3 \times \text{baseline}$ if baseline is abnormal):
 
 Maintain Tenalisib dose and initiate prednisone 40 mg daily. Monitor AST/ALT weekly until resolved and then taper steroid. Withhold Tenalisib in case of development of grade 2 transaminitis or worsening of Grade 1 transaminitis while on steroids. 
Grade 3 Transaminitis ($\text{ALT/AST} >5-20 \times \text{ULN}$; $>5-20 \times \text{baseline}$ if baseline is abnormal):
 
 Withhold Tenalisib and monitor ALT/AST twice a weekly until Grade ≤ 1; restart Tenalisib at one dose lower (Tenalisib 400 mg BID). Initiate prednisone 1 mg/kg in case no improvement after withholding Tenalisib for 1 week. Monitor ALT/AST twice a weekly until Grade ≤ 1; restart Tenalisib at one dose lower (Tenalisib 400 mg BID). and taper steroid. If no immediate response to steroids within 7 days, initiate mycophenolate mofetil. In case of recurrence of transaminitis at reduced doses, discontinue Tenalisib permanently after assessing risk versus benefit. 
Grade 4 Transaminitis ($\text{ALT/AST} >20 \times \text{ULN}$; $>20 \times \text{baseline}$ if baseline is abnormal):
 
 Tenalisib should be permanently discontinued. 
Bilirubin:
 
 Grade 2 ($> 1.5-3 \times \text{ULN}$; $>1.5- 3 \times \text{baseline}$ if baseline is abnormal): Maintain Tenalisib dose. Monitor at least weekly until $\leq 1 \times \text{ULN}$

	
 • Grade 3 ($> 3-10 \times \text{ULN}$; $> 3 - 10 \times \text{baseline}$ if baseline is abnormal): Withhold Tenalisib. Monitor at least weekly until bilirubin is $\leq 1 \times \text{ULN}$; Restart Tenalisib at one dose lower (Tenalisib 400 mg BID). • Grade 4 ($> 10 \times \text{ULN}$; $> 10 \times \text{baseline}$ if baseline is abnormal): Discontinue Tenalisib permanently
Infection	
Grade 3 or higher sepsis or pneumonia
 
 • Withhold Tenalisib until infection has resolved. • Restart at the same or at the reduced dose (Tenalisib 400 mg BID)

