Skin rash (Cutaneous reactions)	
Grade 1-2
 
 • Maintain Tenalisib dose. Initiate supportive care with emollients, antihistamines (for pruritus), or topical steroids • Monitor closely until resolved. 
Grade 3
 
 • Withhold Tenalisib dose. Initiate supportive care with emollients, antihistamines (for pruritus), or topical steroids • Monitor at least weekly until resolved. • Restart Tenalisib at the reduced dose level (Tenalisib 400 mg BID). • If severe cutaneous reaction does not improve, worsens, or recurs, discontinue Tenalisib 
Life threatening or SJS, TEN, DRESS (any grade)
 
 • Discontinue Tenalisib permanently.
Pneumonitis without suspected infectious cause	
Moderate (Grade 2) symptomatic pneumonitis
 
 • Withhold Tenalisib dose. Initiate systemic steroid therapy. If pneumonitis recovers to Grade 0 or 1, Tenalisib may be resumed at reduced dose. • If non-infectious pneumonitis recurs or patient does not respond to steroid therapy, discontinue Tenalisib. 
Severe (Grade 3) or life-threatening pneumonitis
 
Discontinue Tenalisib. Treat with systemic steroid therapy.

Non-infectious Diarrhea	
Moderate diarrhea and responsive to antidiarrheal agents:
 
 • Maintain Tenalisib dose. Monitor at least weekly until resolved. 
Moderate diarrhea and unresponsive to antidiarrheal agents:
 
 • Withhold Tenalisib dose. Initiate supportive therapy with enteric acting steroids (e.g., budesonide). • Monitor at least weekly until resolved. • Restart Tenalisib at the reduced dose level (Tenalisib 400 mg BID). 
Severe diarrhea or hospitalization
 
 • Withhold Tenalisib dose. Initiate supportive therapy with enteric acting steroids (e.g., budesonide) or systemic steroids. • Monitor at least weekly until resolved. • Restart Tenalisib at the reduced dose level (Tenalisib 400 mg BID). 
Life threatening diarrhoea
 
 • Discontinue Tenalisib permanently. •
Cardiac	If a QTcF > 500 msec has been demonstrated, hold dose.

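### The Grade 1-2 transaminitis hold in Table 3 has no restart threshold of its own, and a patient held at Grade 2 already meets the general Grade ≤2 rule in Section 7.5

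*Combined protocol and SAP*

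**What the plan says.** Section 7.5 of the protocol gives a general rule for restarting after any toxicity: "Patients may resume Tenalisib, provided that the toxicity has resolved to Grade" ≤2 or baseline, with no clinical or radiographic sign of progression. The section also says that the tables are guidance, to be applied with the investigator's clinical judgement to events judged related to Tenalisib.

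In Table 3, the Grade 1-2 transaminitis row continues the dose and starts prednisone 40 mg daily. It then says "Monitor AST/ALT weekly until resolved and then taper steroid", followed by "Withhold Tenalisib in case of development of grade 2 transaminitis or worsening of Grade 1 transaminitis while on steroids". The row ends there.

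Other rows set their own recovery level. For Grade 3 transaminitis the instruction is "Withhold Tenalisib and monitor ALT/AST twice a weekly until Grade" ≤1, with restart at 400 mg BID. For Grade 2 pneumonitis it is "If pneumonitis recovers to Grade 0 or 1, Tenalisib may be resumed at reduced dose". For other non-hematologic toxicity at Grade 3 or 4 it is "Withhold Tenalisib dose until toxicity Grade" ≤2.

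The printed ALT/AST ranges are above 1 to 3 times ULN for Grade 1-2 (1.5 to 3 times baseline if baseline is abnormal), above 5 to 20 times for Grade 3, and above 20 times for Grade 4.

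**The concern.** A hold is useful only if the condition for ending it differs from the condition that started it. Here the row orders a hold but does not say when it ends. The general rule that fills the gap is satisfied by the grade that triggered the hold. Section 3.4.5 names raised ALT/AST as an event reported with Tenalisib. Under Section 6.3, visits are three months apart and laboratory tests are left to standard of care, so the row's instructions carry much of the protocol's liver management once an event starts. Two sites following the same text could reasonably act differently: one restarts at an unchanged Grade 2, the other waits for Grade 1 or normal values. A patient with milder transaminitis would also face a weaker restart condition than one with Grade 3.

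**Working it through.** No sample size, power or error rate is involved. The check compares the level that triggers each hold with the level that permits restart.

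**Step 1: does the row supply a threshold?** Its only wording about resolution is attached to weekly AST/ALT monitoring and to the steroid taper. The Grade ≤1 condition and the 400 mg BID dose sit under the Grade 3 heading. The footnote stops treatment after a hold of more than 28 days unless the medical monitor approves, and Section 7.5 calls for discussion with the medical monitor after a delay of more than 2 weeks. Both concern how long a hold lasts; neither sets a recovery level. The general rule is what remains. That it applies is an inference, but no other restart rule is available for this row.

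**Step 2: trigger against restart level.**

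| Hold in Table 3 | Trigger | Restart level | Improvement required? |
|---|---|---|---|
| Grade 1-2 transaminitis, Grade 2 develops | 2 | ≤2 (general rule) | No, 2 ≤ 2 |
| Grade 1-2 transaminitis, worsening Grade 1 | 1 | ≤2 (general rule) | No, 1 ≤ 2 |
| Grade 3 transaminitis | 3 | ≤1 | Yes |
| Grade 2 pneumonitis | 2 | 0 or 1 | Yes |
| Other non-hematologic, Grade 3 or 4 | 3 or 4 | ≤2 | Yes |

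Where Table 3 itself prints Grade ≤2, the hold is at Grade 3 or 4, so that threshold demands a fall.

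**Step 3: how isolated is the gap?** Table 3 contains 12 hold instructions: Grade 1-2 transaminitis, Grade 3 transaminitis, Grade 3 bilirubin, infection, Grade 3 rash, Grade 2 pneumonitis, two for diarrhea, QTcF, and three for other non-hematologic toxicity. Ten print a restart line and one (QTcF) refers the decision to discussion with the medical monitor. The Grade 1-2 transaminitis hold has neither: 12 − 10 − 1 = 1.

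The count of recovery conditions depends on the reading. If monitoring until resolution followed by a restart line counts as a condition, 11 of 12 have one. If it does not, the Grade 3 rash hold and the two diarrhea holds drop out, leaving 11 − 3 = 8.

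**Step 4: the cut-offs.** The Grade 1-2 range ends at 3 times and the Grade 3 range starts above 5 times, for ULN and for an abnormal baseline alike. By the printed numbers, values above 3 and up to 5 times have no action. The catch-all row for other non-hematologic toxicity does not cover them, because transaminitis has its own row.

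**Step 5: the steroid condition.** If it covers both triggers, Grade 2 at onset is treated with prednisone on continued dosing, and the hold applies to Grade 2 reached on prednisone. If it covers only worsening Grade 1, any Grade 2 is held, which conflicts with the row's opening instruction to continue at Grade 1-2. The wording allows both. Step 2 holds either way.

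**The case against.** Five points can be made on the other side.

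- **Resolution implies improvement.** Section 7.5 speaks of toxicity that has resolved to a grade, says that patients may resume, and leaves the tables to the investigator's judgement. A clinician who has just stopped the drug at Grade 2 would probably wait. This stands in part: a reader might infer that the protocol instructs sites to restart without any fall in transaminases, and it does not. It permits that, because no lower threshold is written.
- **The plan tolerates dosing at Grade 2.** Section 3.4.5 asks for interruption at Grade 3 or higher, and the row itself opens by continuing the dose at Grade 1-2. This stands and limits the severity: the Grade 2 hold is an added precaution. It does not explain a hold whose release condition is met at once.
- **The dose is not undefined.** A reader might infer that nothing governs the restart dose. Sections 3.2 and 5.1 keep the patient on the prior dose unless toxicity requires a change, so the prior dose is the default. This stands.
- **The contrast with other rows can be overstated.** The monitoring wording in the rash and diarrhea rows is close to that in this row. This stands for the count of recovery conditions, as Step 3 shows. The absence of any restart line in this row does not depend on that reading.
- **The hold may not follow failure on prednisone.** A reader might infer that every such hold comes after the event progressed on steroids. The text is clear on that only for worsening Grade 1.

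**Conclusion.** The concern holds in a limited form. The Grade 1-2 transaminitis row orders a hold without a restart threshold. The general rule that fills the gap is met at the holding grade and is looser than the rule after Grade 3 transaminitis. The printed cut-offs also leave values above 3 and up to 5 times ULN or baseline without an action. Severity is minor to moderate: a named risk is affected, but the tables are guidance and the investigator may wait. The conclusion assumes that Section 7.5 governs where a row is silent. It also takes the cut-offs as printed, since the documents do not reproduce the CTCAE limits. The documents give no event rate, so the number of patients affected cannot be stated. A reader might infer an effect on the safety summaries or on time to progression; nothing in the documents supports that, and no estimate changes.

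**What to change.** 1. Add to the Grade 1-2 row that after a hold Tenalisib may restart only when ALT/AST is Grade ≤1 or baseline. For a hold at worsening Grade 1, require ALT/AST to be back to, or below, its value when prednisone was started. State in Section 7.5 that this overrides the general Grade ≤2 rule. Grade ≤1 is proposed by analogy with the Grade 3 transaminitis and Grade 2 pneumonitis rows.
2. Make the cut-offs contiguous by assigning values above 3 and up to 5 times ULN or baseline to the Grade 1-2 row, which leaves the Grade 3 boundary where it is. Because the new restart rule depends on grade, also print the boundary between Grades 1 and 2 or refer to CTCAE v5.0, the version in Section 7.1.2.
3. Reword the hold triggers so that it is clear whether the steroid condition applies to both.
4. Optionally, state the restart dose, even if it is simply the prior dose.

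The cost is an edit to the transaminitis rows and one sentence in Section 7.5. It needs no tests beyond the weekly AST/ALT already requested. Some patients will be held longer, in a plan that discourages drug holidays, and a few more may reach the 2-week discussion point or the 28-day limit.
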